	Sweden	Register on persons in nursing homes . Severe Covid-19 risk group was defined as vulnerable individuals being residents at nursing homes (binary status as of 31 December 2020) The Longitudinal integrated database for health insurance and labour market studies . Healthcare personnel defined as healthcare worker occupation status as of 31 October 2018 (binary).	
Comorbidity 1: Chronic pulmonary disease	Denmark	The National Patient Register . Defined as primary diagnoses regardless of type of hospital contact registered before the start date for the country-specific rollout of the fourth vaccine dose (look-back 3 years).	Binary: yes/no (ICD-10 codes: J40-J47, J60-J67, J684, J701, J703, J841, J920, J961, J982, J983)
	Finland	Care register for Health Care . Defined as primary or secondary diagnoses registered prior to the start of the study period.	Binary: yes/no (ICD-10 codes: J41-J44, J47)
	Sweden	National Patient Register . Defined as any recorded ICD-10 diagnosis during inpatient or outpatient contact and before first Covid-19 vaccination (look-back 3 years).	Binary: yes/no (ICD-10 codes: E84, J41-J47, J84, J98)
Comorbidity 2: Cardiovascular conditions	Denmark	The National Patient Register . Defined as primary diagnoses regardless of type of hospital contact registered before the start date for the country-specific rollout of the fourth vaccine dose (look-back 3 years).	Binary: yes/no (ICD-10 codes: I110, I130, I132, I20-I23, I420, I426-I429, I48, I500-I503, I508, I509)
	Finland	Care register for Health Care, Register of Primary Health Care Visits, Special Reimbursement Register and Prescription Centre database . Defined as primary or secondary diagnoses prior to the start of the study period.	Binary: yes/no (ICD-10 codes: I11-I13, I15, I20-I25)

Variable	Country	Data source and details	Values/codes
	Sweden	National Patient Register . Defined as any recorded ICD-10 diagnosis during inpatient or outpatient contact and before first Covid-19 vaccination (look-back 3 years).	Binary: yes/no (ICD-10 codes: I05-I09, I110, I20-I28, I34-I37, I39, I42, I43, I46, I48-I50)
Comorbidity 3: Diabetes	Denmark	The National Patient Register . Defined as primary diagnoses regardless of type of hospital contact registered before the start date for the country-specific rollout of the fourth vaccine dose (look-back 3 years).	Binary: yes/no (ICD-10 codes: E10-E11)
	Finland	Care register for Health Care, Register of Primary Health Care Visits, Special Reimbursement Register and Prescription Centre database . Defined as primary or secondary diagnoses prior to the start of the study period or drug prescriptions before 27 December 2020.	Binary: yes/no (ICD-10 codes: E10, E11, E13-E14; ICPC-2 codes: T89, T90; ATC codes: A10A, A10B)
	Sweden	National Patient Register . Defined as any recorded ICD-10 diagnosis during inpatient or outpatient contact and before first Covid-19 vaccination (look-back 3 years). Swedish Prescribed Drug Register . Antidiabetic drugs use defined as ≥ 2 filled prescriptions during 2020.	Binary: yes/no (ICD-10 codes: E10-E14; ATC code: A10)
Comorbidity 4: Autoimmunity-related conditions ^c	Denmark	The National Patient Register . Defined as primary diagnoses regardless of type of hospital contact registered before the start date for the country-specific rollout of the fourth vaccine dose (look-back 3 years).	Binary: yes/no (ICD-10 codes: D510, D590, D591, D690, D693, D86, E050, E063, E271, E272, G122G, G35, G610, G700, I00, I01, K50, K51, K743, K900, L12, L40, L52, L80, L93, M05, M06, M08, M300, M313, M315, M316, M32, M33, M34, M35, M45)
	Finland	Care register for Health Care, Special Reimbursement Register and Prescription Centre database . Defined as primary or secondary diagnoses prior start of the follow-up or drug prescriptions before 27 December 2020.	Binary: yes/no (ICD-10 codes: D7081, D7089, D80-D84, E250, E271, E272, E274, E310, E896, D86, K50, K51, L40, M02, M05-M07, M139, M45, M460, M461, M469, M941; ATC-codes: H02AB02, H02AB04, H02AB06, H02AB07, L01BA01, L01XC02, L04AA06, L04AA10, L04AA13, L04AA18, L04AA24, L04AA26, L04AA29, L04AA33, L04AA37, L04AB, L04AC, L04AD01, L04AD02, L04AX01, L04AX03)
	Sweden	National Patient Register . Defined as any recorded ICD-10 diagnosis during inpatient or outpatient contact and before first Covid-19 vaccination (look-back 3 years).	Binary: yes/no (ICD-10 codes: D86, G35, K50, K51, L40, M05-M09, M13, M14, M45)
Comorbidity 5: Cancer	Denmark	The National Patient Register . Defined as primary diagnoses regardless of type of hospital contact registered before the start date for the country-specific rollout of the fourth vaccine dose (look-back 3 years).	Binary: yes/no (ICD-10 codes: C00-C85 (without C44), C88, C90-C96)

Variable	Country	Data source and details	Values/codes
	Finland	Care register for Health Care and Special Reimbursement Register. Defined as primary or secondary diagnoses registered within 2 years prior to the start of the study period.	Binary: yes/no (ICD-10 codes: C00–C43, C45–C80, C97, D05.1, D39)
	Sweden	National Patient Register. Defined as any recorded ICD-10 diagnosis during inpatient or outpatient contact and before first Covid-19 vaccination (look-back 3 years).	Binary: yes/no (ICD-10 codes: C00–C96 (without C44), D45–D47)
Comorbidity 6: Moderate to severe renal disease	Denmark	The National Patient Register. Defined as primary diagnoses regardless of type of hospital contact registered before the start date for the country-specific rollout of the fourth vaccine dose (look-back 3 years).	Binary: yes/no (ICD-10 codes: I12, I13, N00–N05, N07, N11, N14, N17–N19, Q61)
	Finland	Care register for Health Care. Defined as primary or secondary diagnoses prior to the start of the study period.	Binary: yes/no (ICD-10 codes: I12, I13, N00–N05, N07, N08, N11, N14, N18, N19, E102, E112, E142)
	Sweden	National Patient Register. Defined as any recorded ICD-10 diagnosis during inpatient or outpatient contact and before first Covid-19 vaccination (look-back 3 years).	Binary: yes/no (ICD-10 codes: I12, I13, N00–N05, N07, N11, N14, N17–N19, Q61)
Influenza vaccination status for season 2023–2024	Denmark	The Danish Vaccination Register. Defined according to the date of influenza vaccine and XBB.1.5-containing vaccine vaccinations.	Categorical (for subgroup analysis only ^d): co-administered on the same date; received influenza vaccine within 1 weeks before to 1 week after XBB.1.5-containing vaccine dose administration but no on same date; no influenza vaccine administered within 1 weeks before to 1 week after of XBB.1.5-containing vaccine dose administration.
	Finland	The National Vaccination Register. Defined according to the date of influenza vaccine (VaxigripTetra or InfluxacTetra) and XBB.1.5-containing vaccine vaccinations.	
	Sweden	The National Vaccination Register. Defined according to the date of influenza vaccine and XBB.1.5-containing vaccine vaccinations.	

9.4 Data sources

All data sources are nationwide registers in native format. All study subcontractors have access to their country-specific data and can link data between registers for the purpose of our study. Given the no-to-very-little lag time of the data source, our analyses will be reflecting real-time information. We will have full data availability for all variables (with no missing data; all the exposures, outcomes, or

covariates are either present or not) during the study period and as reporting to national registers is mandatory/structurally implemented, this provides a near-complete follow-up of all residents over time.

Country/data source	Details
Denmark	
The Civil Registration System [10]	The register provides the unique personal identifier for all permanent residents of Denmark that allows linkage between all Danish health care registers and civil registrations systems. In addition, it holds general demographic information such as birthdate and sex as well as continuously updated information and dates on historical addresses, immigration and emigration status, and death.
The Danish Vaccination Register [9]	The register holds information on all vaccinations administered in Denmark including vaccination date, type/trade name, dose, and product batch number ever since Nov 15, 2015 (where reporting to the register became mandatory). Specifically related to this study, the Danish Health Agency have provided the governmentally assigned Covid-19 vaccine priority groups that were prioritized groups according to the risk of severe infection as well as whether being health and social care workers.
The Danish Microbiology Database [11]	Information on positive PCR tests for SARS-CoV-2 are obtainable via The Danish Microbiology Database (MiBa) that has data on all microbiology samples analyzed at Danish microbiology departments as well as test results, date of sampling, date of analysis, type of test, and interpretation of test. The SARS-CoV-2 PCR tests are freely available to all individuals in Denmark regardless of symptoms status.
The National Patient Register [12]	The register holds information on all hospital contacts in Denmark including the duration of the contact, and diagnoses, which are assigned by the treating physician and registered according to ICD-10 classification system (since 1994).
Finland	
Finnish Population Information System [13]	The register is held by the Digital and Population Data Services Agency and contains personal data on all permanent residents in Finland such as the unique personal identifier, date of birth, place of residence, date of death, and date of immigration, and emigration.
Register of Social Assistance [14]	The register is held by the Finnish Institute for Health and Welfare and contains information on individuals receiving long-term care and/or social assistance (in e.g., nursing homes, people's own homes or other institutions) including social rehabilitation.
Social and Healthcare Professionals Register [15]	The register holds data on individuals right to act as health care personnel.
National Vaccination Register [16]	The register is based on the Register of Primary Health Care Visits and contains information on all Covid-19 vaccinations administered in Finland including date of vaccination, batch number, and trade name.
National Infectious Diseases Register [17]	The register is held by the Finnish Institute for Health and Welfare and contains information on notifiable diseases in accordance with the Finnish Communicable Diseases Act that must be reported by the laboratories and the treating-physicians, or the physician performing an autopsy and hold information on sample dates of all laboratory-confirmed SARS-CoV-2 infections in Finland

Country/data source	Details
National Care Register for Health Care [18]	The register is held by the Finnish Institute for Health and Welfare and comprises information on all inpatient and outpatient hospital contacts in Finland, including admission and discharge dates, whether hospitalization was planned or acute, codes for discharge diagnoses (according to ICD-10) and surgical procedures, and whether discharged as deceased, to own private residence or other health care facilities.
Special Reimbursement Register and Prescription Centre database	These databases are maintained by the Finnish Social Insurance Institution. The Special Reimbursement Register holds information on individuals entitled to special reimbursement for medical expenses. The Prescription Centre database holds information on individuals using selected medications of interest.
Register of Primary Health Care Visits [19]	The register is held by Finnish Institute for Health and Welfare and holds data on all primary health care services delivered in Finland.
Sweden	
The Total Population Register [20]	The register is held by Statistics Sweden and contains data on the unique personal identifier assigned to all individuals in Sweden plus general demographic information such as date of birth, sex, country of birth, place of residence, and date of immigration and emigration.
The Cause of Death Register [21]	The register holds information on date of death and underlying as well as contributing causes of death.
The Longitudinal Integrated Database For Health Insurance And Labour Market Studies (LISA) [22]	The database is held by Statistics Sweden and holds many socioeconomic variables such as data on occupation which we used to identify whether individuals were health care personnel.
Register On Persons In Nursing Homes [23]	The register is held by the National Board of Health and Welfare and holds data on nursing care given in either nursing homes, own homes or other institutions to elderly and/or persons with physical, psychiatric or intellectual disabilities.
The National Vaccination Register [24]	The register is held by the Public Health Agency of Sweden and contains information on administered Covid-19 vaccines in Sweden including data on date of administration, the specific vaccine products, substance, formulation, batch number and dose number (for repeated doses).
Register On Surveillance Of Notifiable Communicable Diseases (Sminet) [25]	The register is held by the Public Health Agency of Sweden and contains information on notifiable diseases (for which reporting is mandatory) reported by either the analysis performing laboratories, the treating physician or autopsy performing physician, in accordance with the Swedish Communicable Diseases Act. Data included are e.g., date of disease occurrence, date of testing, date of positive test, and diagnoses.
The Swedish Patient Register [26,27]	The register is held by the National Board of Health and Welfare and comprises data on all in- and outpatient hospital specialist care in Sweden including data on dates of admission and discharge, whether hospitalization was planned or acute, codes for discharge diagnoses (recorded according to ICD-10-SE) and surgical procedures, whether discharged as deceased, to own private residence or other health care facilities, and type of department.

9.5 Study size (sample size and power)

We expect to be able to include at least 3.1 million individuals who have received a monovalent XBB.1.5-containing Covid-19 vaccine as a fifth or sixth Covid-19 vaccine dose during autumn and winter 2023-24 across the 3 Nordic countries. We will utilize all available data to us from the countries' nationwide registers. The statistical power of our proposed study will be reflected in the 95% CI of the effectiveness estimates. Based on the data the VE results from our recent Nordic studies, we expect to have high statistical precision for the outlined main objectives [28,29].

9.6 Data management

No individual-level data can or will be shared between countries or with EMA. Each country is the sole data owner and controller of their own data. Only aggregated country-specific results will be shared and the final country-combined results reported will be generated using meta-analysis. Data management and statistical analyses will be conducted using a Common Data Model (CDM). The analytical group in Denmark will code the statistical analyses using R-scripts (R version 4.2.2.). The R-scripts will be made available on GitHub (also during the programming phase to facilitate input and comments). The analysts in each of the participating countries will then run the R-scripts and return the output to Denmark for meta-analysis.

[figure not shown]
[figure not shown]
9.7 Data analysis

Procedures

We will use a matched study design to evaluate the effectiveness of receiving a monovalent XBB.1.5-containing Covid-19 vaccine in comparison with not receiving a Covid-19 vaccine during the autumn and winter 2023-24. Individuals who during the study period receive an XBB.1.5-containing Covid-19 vaccine as either a fifth or sixth dose will be matched on the day of vaccination with individuals who have not yet received a fifth or sixth dose, respectively. Individuals will be matched on age (5-year bins), calendar time of last mutual vaccine dose (i.e., either 4th dose for the 5 vs 4- or 5th dose for the 6 vs 5-matched pairs), sex, region of residence, vaccination priority groups (i.e., individuals at high-risk of severe Covid-19), number of selected comorbidities (0, 1, 2, ≥ 3 of chronic pulmonary disease, cardiovascular conditions, diabetes, autoimmunity-related conditions, cancer, and moderate to severe renal disease). The day the XBB.1.5-containing Covid-19 vaccine was administered within each matched pair will serve as the index date for both individuals. If individuals who were included as a matched XBB.1.5-containing vaccine-unvaccinated individual (i.e., a reference individual) receive an XBB.1.5-containing vaccine later than the assigned index date, they will be allowed to potentially re-

enter as an XBB.1.5-containing vaccine recipient in a new matched pair on that given date and the follow-up for the current pair will be censored.

We will follow individuals from one week after the index date (to ensure full immunization among XBB.1.5-containing Covid-19 vaccine recipients) up until the day of an outcome event, end of week 18 (end of week 24 if possible) since the index date, receipt of additional Covid-19 vaccine dose, death, emigration, or end of the study period, whichever occurs first. The date of vaccination is denoted as the index date. The start of the follow-up period will commence on Day 0, corresponding to eight days after the index date. The figure below illustrates the study cohort construction, as an example of the comparison fifth vs fourth dose.

Statistical analysis

We will use 1:1 exact matching without replacement with the prespecified covariates to find a precise pairing of individuals receiving a monovalent XBB.1.5-containing Covid-19 vaccine to individuals not receiving a Covid-19 vaccine.

Cumulative incidences will be estimated by the Aalen-Johansen estimator using death as a competing risk, and from these we will calculate the comparative VE as 1 – risk ratio at end of week 6 and 18 (or

24). The corresponding 95% CI will be calculated using the delta method. Country-specific estimates will be combined by random-effects meta-analyses implemented using the *mixmeta* package in R.

Comparative waning will be estimated using meta-regression [30]. First, we will estimate the VEs (in the specific comparison being evaluated) in each consecutive 6-week intervals (week 1-6 (day 0-42), 7-12 (day 43-84), 13-18 (day 85-126) and 19-24 (day 127-168)) by stratification on time since XBB.1.5-containing Covid-19 vaccine vaccination. Second, we will regress the VE estimates on time-since-vaccination in 6-week intervals using meta-regression in the form of an intercept and a slope coefficient. The estimated slope coefficient will represent the percentage point change in VE per 6 weeks since vaccination.

Subgroup analyses will be conducted according to sex, age groups (</≥75 years), and influenza vaccination status for XBB.1.5-containing Covid-19 vaccine vaccinated (1)co-administered on the same date, 2) received influenza vaccine within 1 weeks before to 1 week after XBB.1.5-containing vaccine dose administration but no on same date, and 3) no influenza vaccine administered within 1 weeks before to 1 week after of XBB.1.5-containing vaccine dose administration).

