Treatment strategies	
 1) Receive a monovalent XBB.1.5-containing Covid-19 vaccine at baseline and do not receive additional Covid-19 vaccine doses during follow-up 2) Do not receive a monovalent XBB.1.5 -containing Covid-19 vaccine at baseline and continue being unvaccinated during follow-up 	Same as for the target trial. We define the date of XBB.1.5-containing Covid-19 vaccine vaccination (that is, the index date) according to the registered date of administration.
Treatment assignment	Individuals are randomly assigned to a strategy at baseline in a 1:1 ratio	Individuals are assigned to the strategy compatible with their treatment received at that time (XBB.1.5 vaccinated and - unvaccinated); randomization is assumed conditional on matching (in a 1:1 ratio) on baseline covariates; XBB.1.5-unvaccinated are assigned the index date of the matched XBB.1.5 vaccine recipient.
Outcomes	
Covid-19 hospitalization: inpatient hospitalization with a registered Covid-19-related diagnosis and a positive PCR test for SARS-CoV-2 (within 14 days before to 2 days after the day of admission)
 
Covid-19 death: death within 30 days of a positive PCR test for SARS-CoV-2
	Same as for the target trial.

Follow-up	Follow-up for each individual will start at day 8 from treatment assignment (to ensure full immunization among XBB.1.5-containing Covid-19 vaccine recipients) and end on day of outcome event, week 18 (week 24 if possible) has passed, death, emigration, or end of the study period (date of latest data availability as of 31 March 2024), whichever occurs first.	Same as for the target trial.
Causal contrast of interest	Per-protocol	Observational analog to per-protocol effect.

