9.2 Setting

Eligibility criteria for study inclusion are:

- 1) Aged of 65 years or older as of the study start
- 2) Have a known residency within the specific country at start of study period (1 October 2023)
- 3) Have received four or five Covid-19 vaccine doses (of AZD1222, BNT162b2, or mRNA-1273 vaccines only [AZD1222 as part of the primary vaccination course only; an original/bivalent BA.4-5/BA.1 mRNA vaccine as the fourth/fifth vaccine dose] prior to start of study period
- 4) No history of Covid-19 hospitalization prior to start of study period

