9.8 Supplementary analyses and quality control

Quality control will be conducted indirectly to evaluate the validity of our main analyses by 1) making sure that the prevalence of the different schedules and the number of study endpoints match national surveillance dashboards and reports, 2) descriptive and analytical results are compatible with our previous findings, and 3) using a Common Data Model (CDM), by which national register data are standardized to a common structure, format and terminology in order to allow the same statistical programming scripts to be used in each country. The use of a CDM with common statistical programming scripts will facilitate efficient use of resources and reproducibility of the statistical analyses. We will ensure the scientific quality of the work, by division of review tasks (including statistical code review) and responsibilities in a timely fashion and by adhering to the ENCePP Code of Conduct (see attachment). We will perform matching quality diagnostics to assess the control of matched parameters. We will include a sensitivity analysis where we start follow-up after 3 weeks (21 days) after the index date to further reduce the potential of transient healthy vaccinee effect around the time of vaccination as well as *spill-over effect* (that is, prior to the index date) given that some severe Covid-19 events may take longer time to develop.

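### Nothing keeps hospital inpatients out of the matched pairs at the index date, which can overstate early VE (most clearly against Covid-19 death) and mimic waning

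*Protocol*

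**What the plan says.** Eligibility (sections 9.1 and 9.2) is assessed once, at 1 October 2023. Its only hospital criterion is "No history of Covid-19 hospitalization prior to start of study period". Pairs are formed later: under the emulation table in 9.1, "XBB.1.5-unvaccinated are assigned the index date of the matched XBB.1.5 vaccine recipient". According to 9.7, recipients "will be matched on the day of vaccination with individuals who have not yet received a fifth or sixth dose", and the match is on 5-year age bin, timing of the last shared dose, sex, region, priority group and number of selected comorbidities.

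Follow-up starts eight days after the index date (9.7). Section 9.8 adds a sensitivity analysis that starts at 21 days "to further reduce the potential of transient healthy vaccinee effect around the time of vaccination" and to limit spill-over of events that began before the index date.

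The two outcomes (9.3) treat a current stay differently. Covid-19 hospitalization is a first inpatient stay with a positive PCR between 14 days before and 2 days after admission. Covid-19 death is any death within 30 days of a positive PCR; it needs no admission, and the PCR need not come after the index date.

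**The concern.** The emulation assumes that, given the matching factors, who is vaccinated on the index date is as good as random. Being acutely ill in hospital that day plausibly lowers the chance of vaccination and raises the risk of a severe outcome, and none of the matching factors can show it:

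- Danish comorbidities predate the roll-out of the fourth dose, and Swedish diagnoses predate the first vaccination. Finnish diagnoses mostly stop at the start of the study period.
- Risk-group status was last updated on 24 May 2021 in Denmark. Finnish 24-hour care status is that of 27 December 2021. Swedish nursing-home residence is a "binary status as of 31 December 2020".
- The diagnostics in 9.8 assess the matched parameters only, so they would not reveal this imbalance.

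Two objectives are exposed. An excess of high-risk references raises VE (objective 1). If the excess fades with time since index, VE falls from one 6-week interval to the next even when true protection is constant, and the meta-regression slope of objective 2 turns negative.

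**Working it through.** The Protocol gives no figure on this point, so there is none to reproduce. The size can only be bounded under assumptions.

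**Inputs, all assumed.** f and g are the shares of references and recipients who are inpatients on the index date. k is their risk of the outcome relative to everyone else. True VE is 60% and constant; the background in section 7 cites 55.4% to 76% against hospitalization.

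**Formula.** Observed VE = 1 - (1 - VE) × (1 + g(k-1)) / (1 + f(k-1)). With three equally spaced intervals, the least-squares slope is (third - first)/2.

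**General case, g = 0, k falling over three 6-week intervals**

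| f | k by interval | Observed VE (%) | Slope, points per 6 weeks |
|---|---|---|---|
| 0.5% | 5, 2, 1.5 | 60.8, 60.2, 60.1 | -0.3 |
| 1% | 5, 2, 1.5 | 61.5, 60.4, 60.2 | -0.7 |
| 1% | 10, 4, 2 | 63.3, 61.2, 60.4 | -1.5 |
| 2% | 10, 4, 2 | 66.1, 62.3, 60.8 | -2.7 |

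Example, second row, first interval: 1 - 0.40/(1 + 0.01 × 4) = 1 - 0.40/1.04 = 61.5%.

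If recipients have half the inpatient share (f = 1%, g = 0.5%, k = 5), the first interval is 1 - 0.40 × 1.02/1.04 = 60.8%. To read 62% with g = 0, f(k-1) must be 0.40/0.38 - 1 = 0.053; to read 65%, 0.40/0.35 - 1 = 0.143.

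**Covid-19 death, one specific route.** A person admitted with Covid-19 after 1 October still passes eligibility and can be drawn as a reference. If death follows from day 8 onwards and within 30 days of the PCR, it counts against the reference arm. Assume 0.05% of references are such inpatients and 10% of them die in that period: the added risk is 0.0005 × 0.10 = 0.00005. With a reference risk of 0.05%, VE reads 1 - 0.40 × 0.0005/0.00055 = 63.6%. With 0.1%, it reads 1 - 0.40 × 0.001/0.00105 = 61.9%.

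**Covid-19 hospitalization, the opposite force.** A stay already running at index generally cannot become a qualifying event, because the PCR must fall close to the admission day. During that stay k = 0, and f = 1% gives 1 - 0.40/0.99 = 59.6%. If 80% of the inpatients' time in weeks 1-6 is spent in that stay and k = 5 otherwise, average k = 0.2 × 5 = 1 and VE reads 60.0%: no net bias.

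**What the delayed start achieves.** With an assumed exponential residual stay averaging 5 to 12 days, the share still in hospital is exp(-8/5) = 20% to exp(-8/12) = 51% at day 8, and exp(-21/5) = 1.5% to exp(-21/12) = 17% at day 21.

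**The case against.** The strongest reply is that the plan already targets this kind of bias. Follow-up starts on day 8, a 21-day start is prespecified for a transient healthy vaccinee effect, and 9.9 names confounding as a potential major concern. By day 21 few index-day inpatients would still be in hospital. That stands as mitigation, but it is partial. Delay leaves the same people in the reference arm, the 21-day start is not the main analysis, and a death on days 21 to 30 after a PCR near the index date still counts.

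It can also be said that the inputs are invented and that the milder ones give small effects. This stands too: inpatient shares and relative risks are nowhere in the document. A reader might reach for a larger figure, for example shares of 1.5% and 0.1% with a relative risk held at 15: the factor is 1.21/1.014 = 1.193 and VE reads 66.5%. But that holds constant an excess that the argument says fades. If the relative risk runs 15, 8, 4 (mean 9), the factor is 1.12/1.008 = 1.11 and VE reads 64%.

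A reader might further infer that VE is overstated for both outcomes, or that inpatients cannot be vaccinated at all. The document supports neither. Its hospitalization definition pushes the other way during the index stay, and it is silent on vaccination in hospital.

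Finally, the cohort-construction figure in 9.7 could not be read for this check. A condition shown only there would still need to be stated in the text.

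**Conclusion.** The gap is real: the written plan has no inpatient or recent-admission condition at the index date for either arm, and no matching factor stands in for one. Provided inpatients are under-represented among recipients and at raised risk, early VE against Covid-19 death can be overstated and a constant VE can appear to wane. For Covid-19 hospitalization the sign is open.

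Under the milder assumptions the error is at most about 1.5 VE points in weeks 1-6 and 0.7 points of slope per 6 weeks. Under the heavier ones it is about 3 to 6 points and 1.5 to 2.7 points of slope. These ranges illustrate and do not estimate. The change is worth making because section 9.5 expects high precision from at least 3.1 million recipients, so a systematic shift of this order need not be hidden by sampling error, and because the exclusion deals with either direction.

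**What to change.** In 9.7 and in the emulation table of 9.1, add an index-date condition for both members of a pair, in the main analysis: not an inpatient for any cause on the index date, and no discharge within a short prespecified window before it. Fourteen days is one option; it is a judgement and should be varied in sensitivity analysis. Report the number excluded by arm, which would also show whether the imbalance exists. Repeat the waning meta-regression with the 21-day start.

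With f = g = 0 the formula returns the true VE and a zero slope, as far as current inpatients go; risk that stays raised beyond the discharge window would remain.

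The data are at hand. For Denmark, 9.4 states that "The register holds information on all hospital contacts in Denmark including the duration of the contact", and it lists admission and discharge dates for the Finnish and Swedish hospital registers. The Swedish register delay adds no new constraint, since the filter needs data only up to the index date and the outcome needs later data from the same register. The cost is one date filter in the common R-script, a small loss of potential references, and results that apply slightly less widely, to people not in or just out of hospital.
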